“Should COVID-19 Quantitative Antibody Titers be Implemented to Guide COVID-19 Booster Vaccinations Regardless of HIV status, Immunosuppression, or Age?”

**Study Protocol
Version 2.5**

.....

Prepared by:

[name], [name], and [name]

October 29, 2021

Table of Contents

Contents

1. SYNOPSIS	3
2. INTRODUCTION	4
BACKGROUND	4
RATIONALE FOR THE STUDY	6
3. RESEARCH OBJECTIVES	7
PRIMARY OBJECTIVE(S)	7
SECONDARY OBJECTIVE(S)	7
4. DATA SOURCE	8
AHF MIDTOWN MANHATTAN HEALTHCARE CENTER	8
DESCRIPTION OF THE DATABASE AND PREPARATION OF ANALYTICAL FILES	8
5. STUDY POPULATION	11
INCLUSION CRITERIA	11
EXCLUSION CRITERIA	11
6. STUDY DESIGN	12
OVERVIEW OF STUDY DESIGN	12
EXPOSURES OF INTEREST	12
SUBGROUPS OF INTEREST	12
STUDY ENDPOINTS	12
STUDY COVARIATES	13
7. STATISTICAL ANALYSIS	14
ANALYSIS OF DEMOGRAPHICS/BASELINE CHARACTERISTICS	14
ANALYSIS OF PRIMARY OBJECTIVES	14
ANALYSIS OF SECONDARY OBJECTIVES	15
SENSITIVITY ANALYSES	15
SUBGROUP ANALYSES	16
8. STUDY CONDUCT	17
REGULATORY AND ETHICAL CONSIDERATIONS	17
INFORMED CONSENT	17
DATA PRIVACY & PERSONALLY IDENTIFIABLE INFORMATION (PII)	17
ADVERSE EVENT REPORTING	17
9. ADMINISTRATIVE MATTERS	18
QUALITY ASSURANCE	18
10. REFERENCES	19

1. Synopsis

Little real-world data are available on the antibody response after COVID-19 vaccination in HIV-negative and HIV-positive individuals, the potential usage of quantitative antibody testing to determine those at greatest risk for infection while helping guide additional vaccination timing, and the antibody response of vaccine boosting in individuals with no response or low response to initial vaccinations. At the moment, clinicians must rely on general category recommendations and clinical judgement when advising their patients on the utility of vaccine boosting, as well as their level of protection from COVID vaccination. Real-world evidence is needed to better inform such decisions. The aim of this study is to assess levels of COVID-19 vaccine response through measuring surrogate Ig spike antibody measurements, to determine the rates of antibody level decay after vaccination, and to measure the efficacy of utilizing these antibody measurements to help guide the timing of booster doses among HIV-negative and HIV-positive patients.

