Limited real-world data are available on the antibody response after COVID-19 vaccination comparing HIV-negative and HIV-positive individuals. There are also limited information that would allow the potential usage of quantitative antibody testing to determine those at greatest risk for infection while could help in guiding the timing of additional vaccinations. There are also limited information on the antibody response of vaccine boosting in individuals, especially those with altered immune response that might lead to no response or low response to the primary vaccination series. At the moment, clinicians must rely on clinical judgement when advising their patients on the utility of vaccine boosting, as well as their level of protection from COVID vaccination. Additional information would be helpful in informing decisions on third doses in different populations such as HIV positive people, whose responses to COVID-19 vaccine and immune status would help define the timing and need for an additional vaccination based on current recommendations. Real-world evidence is needed to better inform such decisions.

3. Research Objectives

PRIMARY OBJECTIVE(S)

Objective #1: Describe COVID-19 vaccine response including frequency of non-response, low response, and adequate response as measured by antibody test by HIV status (e.g., rates, and relationship to demographic and clinical characteristics, as well as vaccine types)

Objective #2: Describe rate of decline in antibody levels over time by HIV status, vaccine type, and baseline CD4 count after initial vaccination as well as other parameters.

SECONDARY OBJECTIVE(S)

Objective #3: Describe response to COVID-19 boosters given (vaccine types, concordant vs. discordant boosters, duration from initial vaccine completion, antibody response, and side effects)

Objective #4: Describe rate of decline in antibody levels over time by HIV status, baseline CD4 count, by vaccine given, and after booster vaccination

Objective #5: Recording breakthrough infections after vaccinations and assessing antibody levels pre-breakthrough infection

4. Data Source

AHF MIDTOWN MANHATTAN HEALTHCARE CENTER

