The design for this study is an observational cohort study utilizing prospectively collected electronic medical record (EMR) data from usual clinical care at AHF Midtown Manhattan Healthcare Center, obtained from the OPERA® Observational Database.

The study population will consist of adults vaccinated against SARS-CoV-2 virus receiving the Roche SARS-CoV-2 Semi-Quant Spike Ig AB test as part of their usual clinical care. These individuals will be followed from vaccination until study end.

EXPOSURES OF INTEREST

Initial vaccination with Pfizer, Moderna, and J&J COVID vaccines, booster vaccination with Pfizer, Moderna, and J&J vaccines, and concordant boosting versus discordant boosting

SUBGROUPS OF INTEREST

HIV-positive versus HIV-negative patients, individuals with at least 2 measurements of antibody levels, and boosted individuals are the subgroups of interest.

STUDY ENDPOINTS

Endpoints for both the primary and secondary objectives are non-responders and low responders and rates of decline of SARS-CoV-2 antibodies

- Non-response will be defined as: 0 to <50 U/mL
- Low response will be defined as: ≥ 51 to ≤ 250 U/mL
- Adequate response will be defined as: >251 U/mL

Roche's Elecsys semi-quantitative spike Ab Ig assay is a commercially available assay that can potentially be utilized to help guide the need for an additional vaccination dose based upon the levels of antibodies that have been previously clinically correlated with neutralizing antibodies. As part of routine care, Ab Ig assays were performed for some patients at the AHF Midtown Manhattan Healthcare Center and results were recorded in their EHR.

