To normalize across different neutralization assays utilized in phase 3 studies of various COVID-19 vaccines, Khoury, et al., estimated that a 50% protective neutralization level equivalent to 20% of the mean titer in the convalescent subjects equates to a measured in vitro neutralization titer of between 1:10 and 1:30 was approximated at 54 international units IU/ml (95% CI 30–96 IU/ml) against wild-type CoV-19 infection.^{xx} During the period of COVID-19 infection where the Delta virus predominated, a quantitative spike Ab's >250 IU/mL was deemed adequate, based on studies that show that an antibody titer of 4-6x wild-type SARS-CoV-2 were required to effectively neutralize Delta viral strains.^{xxi,xxii, xxiii} We thus utilized a threshold level of >250 (5x wild-type ab levels) IU/mL as an adequate vaccine response against circulating Delta virus post last vaccination recommended in a series, a level of <50 IU/mL as a non-responsive post vaccination titer (inadequate for even wild-type Co-V-2 infection), and levels between (50-250 IU/mL) as a low vaccine response. Non and low-responders who had Co-V-2 Spike Ig levels that were inadequate based on the correlation of Spike Ig levels and neutralizing ab correlations relative to the predominant circulating viral strains were offered optional booster vaccinations with subsequent antibody response measurement post vaccination as standard of care. These recommendations are the current one's implemented during the Delta Co-V-2 19 outbreak by the Ministry of Solidarity and Health of France and the COVID Guidelines group in Geneva, where 260 IU/mL and 300 IU/mL, respectively, are considered gray zones of antibody protection against the Delta virus and where booster vaccinations are recommended for consideration.^{xxiv, xxv}

STUDY COVARIATES

Covariates of interest include: age, sex, race, ethnicity, HIV status, region, payer, immunosuppressive conditions, CD4 cell count, comorbid conditions, BMI. This information will be obtained from each patient's electronic health records.

7. Statistical Analysis

ANALYSIS OF DEMOGRAPHICS/BASELINE CHARACTERISTICS

Demographic and clinical characteristics will be summarized in the overall population using medians with interquartile ranges (IQR) for continuous variables and frequencies with proportions for categorical variables.

ANALYSIS OF PRIMARY OBJECTIVES

Objective #1: COVID-19 vaccine non-response and low response as measured by antibody test by HIV status

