In the sub-population of Individuals who received a COVID vaccine booster, the following characteristics will be described using medians with interquartile ranges (IQR) for continuous variables and frequencies with proportions for categorical variables: initial and booster vaccine types, concordant vs. discordant boosters, duration between initial vaccine completion and booster dose, antibody response after the booster, and side effects recorded. Post vaccination responses will be determined no earlier than 2 weeks post vaccination.

Objective #4: Rate of decline in antibody levels over time by HIV status, booster type, and baseline CD4 count after booster vaccination

Rates and 95% confidence intervals for changes in antibody levels will be estimated using linear regression, among individuals with at least two antibody measurements, including one after the booster dose. Univariate linear regression, will be employed, using the continuous antibody level as the dependent variable, and timing of tests as the dependent variable. Robust variance estimator will be used to account for repeated measures. Rates of decay will be produced overall, and stratified by HIV status, booster type and baseline CD4 cell count.

Objective #5: Recording breakthrough infections after vaccinations and assessing antibody levels pre-breakthrough infection

Among all individuals with full vaccination and antibody testing, the EHR will be searched for documentation of COVID infection after vaccinations. If breakthrough infections are observed, antibody levels prior to infection will be described. Note: COVID infections may not be recorded in the EHR if diagnosed outside of the clinic.

SENSITIVITY ANALYSES

NA

SUBGROUP ANALYSES

Patients provided COVID boosters will be evaluated by the types and combinations of vaccines they received. Further, patients given sequential antibody tests will be evaluated by vaccine type for response over time.

8. Study Conduct

REGULATORY AND ETHICAL CONSIDERATIONS

OPERA® complies with all HIPAA and HITECH requirements and has received annual institutional review board (IRB) approval by Advarra IRB, including a waiver of informed consent and authorization for use of protected health information

INFORMED CONSENT

Informed consent has been waived for this non-interventional, observational research and authorization for use of the protected health information has been approved by Advarra IRB.

DATA PRIVACY & PERSONALLY IDENTIFIABLE INFORMATION (PII)

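### Objective #3 describes post-booster antibody response without the pre-booster response level, so it cannot show how prior non-responders and low responders respond to a booster, an evidence gap the Synopsis names

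*Combined protocol and SAP*

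**What the plan says.** Section 1 (Synopsis) lists three areas where real-world data are scarce. One is "the antibody response of vaccine boosting in individuals with no response or low response to initial vaccinations". The Synopsis also states an aim "to measure the efficacy of utilizing these antibody measurements to help guide the timing of booster doses among HIV-negative and HIV-positive patients".

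Section 3 words the objective more broadly: "Describe response to COVID-19 boosters given (vaccine types, concordant vs. discordant boosters, duration from initial vaccine completion, antibody response, and side effects".

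Section 6 (Study Endpoints) defines non-response, low response and adequate response by titre and applies these endpoints to the secondary objectives as well. It adds that patients in the two lower categories "were offered optional booster vaccinations with subsequent antibody response measurement post vaccination as standard of care".

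Section 7, Objective #3, sets the analysis: "In the sub-population of Individuals who received a COVID vaccine booster, the following characteristics will be described". After vaccine types and concordance, the list ends with "duration between initial vaccine completion and booster dose, antibody response after the booster, and side effects recorded". The Subgroup Analyses add: "Patients provided COVID boosters will be evaluated by the types and combinations of vaccines they received". Section 6 lists the subgroups in general: "HIV-positive versus HIV-negative patients, individuals with at least 2 measurements of antibody levels, and boosted individuals are the subgroups of interest".

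**The concern.** Booster response in people who responded poorly to the primary series can be read only against where each person started. The Objective #3 list records where patients ended. A patient already above 250 before the booster and still above it afterwards adds to the adequate count just as a non-responder who converted does. The summary then depends on the mix of starting categories among those boosted, and the plan does not report that mix.

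The same applies to the concordant and discordant groups. If their starting titres differ, their post-booster summaries will differ for that reason alone. At stake is whether the study can speak to a gap it raises itself, and one that bears on its aim of using titres to guide booster timing.

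**Working it through.** **Text check**

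1. Question: booster response in prior non- and low responders (Section 1). Section 6 says that these patients were offered boosters and then measured.
2. Analysis set: all boosted patients (Section 7, Objective #3). Nothing limits it by prior titre.
3. Variables: the only antibody item is the response after the booster. There is no pre-booster titre, category or change.
4. Breakdown: vaccine type and combination (Section 7, Subgroup Analyses). Prior response is not among the Section 6 subgroups.
5. Eligibility: Section 5 asks for a test after full vaccination. It does not say that the test must precede the booster, so a patient whose only test follows the booster can qualify.
6. Other routes: Objective #4 needs at least two measurements, one of them after the booster, so a pre-booster titre can enter. It enters as a point in a linear regression on time, with strata for HIV status, booster type and CD4 count. Sequential tests are otherwise evaluated by vaccine type. Objective #1 assigns the response categories, but nothing links them to the post-booster result.

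**Size**

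The documents give no number boosted, no mix of starting categories and no expected response, so there is no plan figure to reproduce. All inputs below are assumed: 100 boosted patients; 40 non-responders, 40 low and 20 adequate before; 85 adequate after, with all 20 staying adequate.

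- Pooled: 85/100 = 85%.
- Non- and low responders combined: (85 − 20)/(40 + 40) = 65/80 = 81.25%, which is 3.75 points below the pooled figure.
- Not adequate after the booster: 100 − 85 = 15, all among those 80.
- Non-responders alone, if all 15 are theirs: (40 − 15)/40 = 25/40 = 62.5%.
- Non-responders alone, if none are theirs: 40/40 = 100%, with low responders then at 25/40 = 62.5%.

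More generally, let P be the pooled adequate share and w the share of boosted patients who were non- or low responders before. The adequate share within that combined group lies between max(0, (P − (1 − w))/w) and min(1, P/w). For P = 90% and w = 50%, the lower limit is (0.90 − 0.50)/0.50 = 80%.

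| Pooled P | w = 10% | w = 25% | w = 50% | w = 75% | w = 100% |
|---|---|---|---|---|---|
| 80% | 0–100% | 20–100% | 60–100% | 73.3–100% | 80% |
| 90% | 0–100% | 60–100% | 80–100% | 86.7–100% | 90% |
| 95% | 50–100% | 80–100% | 90–100% | 93.3–100% | 95% |

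Where the formula is not cut off at 0, the lower limit is the value reached when every previously adequate patient stays adequate. The pooled and subgroup figures are certain to agree only at w = 100%, which the documents do not state.

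**The case against.** The strongest reply is that Objective #3 as worded covers all boosters given, so an all-boosted population matches it. That stands: the non- and low-responder question is one of three gaps in the Synopsis, not the text of the objective. A reader might infer that Objective #3 fails its own stated question; the documents do not support that.

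Second, a reader might infer that the plan ignores pre-booster titres altogether, or that patients with adequate titres were in fact boosted and raise the result. Neither is shown. Objective #4 can use pre-booster titres. The documents say only that non- and low responders were offered boosters; patients with adequate or unknown titres are not excluded, but nothing says how many there were. If nearly all boosted patients were non- or low responders, the pooled figure would be close to their combined figure. It would still merge titres below 50 with those of 50 to 250, although Section 6 calls the lower group inadequate even for wild-type virus.

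Third, the illustration depends on the target. For the two groups together the difference is only 3.75 points; the wide range belongs to non-responders alone, and its ends are extreme allocations. That stands. So does the point that the plan does not say post-booster response will be reported as a percentage adequate. A median titre over the same mixture would have the same limitation.

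Last, the objective is secondary and descriptive, no test of concordant against discordant boosters is specified, and the table could be added later without loss of data. This limits the severity but does not close the gap.

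**Conclusion.** The point holds as a mismatch between an evidence gap named in the Synopsis and the analysis planned for Objective #3. As written, no analysis in Section 7 reports post-booster response by prior response level. This does not invalidate Objective #3 as a description of boosters given.

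The size is unknown, because the mix of starting categories is not given. On the assumed mix, the pooled 85% overstates the combined non- and low-responder result by 3.75 points and leaves the non-responder result undetermined between 62.5% and 100%. The change is worth making before analysis: the categories are already defined and the remedy is one table.

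**What to change.** For Objective #3 only, define a booster-response set: boosted patients with an eligible titre after the primary series and before the booster, and an eligible post-booster titre. Then:

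- Tabulate post-booster category and paired change by the last pre-booster category (non, low, adequate), overall and by concordant versus discordant booster. Specify the last titre, because an earlier one may fall in a different category after decay.
- Report paired change on a scale that handles values of 0 or below the assay limit. A simple fold-change is undefined at 0, which the non-response category includes.
- Show boosted patients with no pre-booster titre as a separate row.
- Label the table descriptive. Grouping on a low starting titre is subject to regression to the mean, and there is no unboosted comparator.

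Do not require a pre-booster titre for Objective #4; decline after a booster can be estimated from post-booster titres, and the restriction would lose patients.

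To define an eligible post-booster titre, the Synopsis (at least 3 weeks after the booster) and Section 7, Objective #3 (no earlier than 2 weeks) must be reconciled.

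The cost is protocol and SAP wording plus one cross-tabulation of data drawn from the EHR. The downside is a smaller main booster-response table.

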The study population will include adults who were fully vaccinated against SARS-CoV-2 virus (i.e., two doses of Pfizer or Moderna vaccines or one dose of the J&J vaccine), and have received a Roche SARS-CoV-2 Semi-Quant Spike Ig Ab test at least 3 weeks after full vaccination as part of their usual clinical care at AHF Midtown Manhattan Healthcare Center.

Incidence rates of COVID vaccine response levels (i.e., adequate, low, non-response) will be estimated using univariate Poisson regression, overall and by vaccine type. Among individuals with at least two antibody measurements, rates of antibody levels decay will be estimated using univariate linear regression, overall and stratified by HIV status, vaccine type and baseline CD4 cell count. In the sub-population of individuals who received a COVID vaccine booster, vaccination and antibody response will be characterized at least 3 weeks after the booster is received. Univariate linear regression will be used to estimate rates of antibody levels decay, among individuals with at least two antibody measurements, including one after the booster dose. Rates of response decay will be produced overall, and stratified by HIV status, booster type and baseline CD4 cell count.

2. Introduction

BACKGROUND

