The standardization of the data to common terms and application of the Evidian knowledge base are key process steps in gathering data from multiple heterogeneous EHR systems and databases from many locations into a single, homogenous OPERA database for conducting research and commercial analyses. The patient health data gathered, classified and aggregated includes complete medical history & social history, visit dates, vital signs, lab orders and results, medications, problems & diagnoses, and procedures.

Evidian has developed rigorous data management processes that include both automated and manual quality checks. Data quality methods include common techniques such as:

- Detection and reporting of outliers that lead to correction, acceptance, or exclusion of observations; these can include a medical review.
- Detection of potentially missing data (e.g., a patient taking ART medications with no history of HIV infection to determine whether the use was prophylactic or treatment for infection diagnosed elsewhere).
- Data completion using multiple observations and sources (e.g., using diagnoses codes, free text, past medical history, etc. to determine if patient is naive to HIV therapy).
- Detection of observations that are known to be (or likely to be) mutually exclusive for a patient (e.g., record of medications that are typically not administered concurrently).

5. Study Population

Individuals presenting for care at AHF Midtown Manhattan Healthcare Center and followed through their electronic health records in the OPERA Observational Database.

INCLUSION CRITERIA

Patients who were:

1. Cared for at AHF Midtown Manhattan Healthcare Center and followed in the OPERA observational database
2. Active in care in the last 24 months
3. Fully vaccinated against SARS-CoV-2 virus, implemented as 21 days after the second Pfizer or Moderna injections, 21 days after the one J&J injection
4. Received a Roche SARS-CoV-2 Semi-Quant Spike Ig AB test after full vaccination as usual clinical care
5. ≥ 18 years of age at vaccination

EXCLUSION CRITERIA

Patients who were:

1. Unvaccinated or partially vaccinated against SARS-CoV-2 virus
2. Never tested with a SARS-CoV-2 Semi-Quant Total AB test after full vaccination

6. Study Design

OVERVIEW OF STUDY DESIGN

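### Objective #4 does not say whether pre-booster values enter its slope; on the natural reading the slope is not post-booster decay

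*Combined protocol and SAP*

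**What the plan says.** Section 3 gives Objective #4 as: "Describe rate of decline in antibody levels over time by HIV status, baseline CD4 count, by vaccine given, and after booster vaccination". The Section 7 heading for the same objective is "Rate of decline in antibody levels over time by HIV status, booster type, and baseline CD4 count after booster vaccination". Both name decline after the booster as the target.

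The analysis set is wider than that target. Section 7 takes patients "among individuals with at least two antibody measurements, including one after the booster dose", and the Synopsis says the regression will "estimate rates of antibody levels decay, among individuals with at least two antibody measurements, including one after the booster dose". Only one of the two tests has to follow the booster.

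The model is one univariate linear regression of the continuous antibody level on the timing of tests, with a robust variance for repeated measures. The time variable is labelled as dependent, as is the antibody level, and no origin is given for it. There is no booster term or change-point. The methods sentence speaks of changes in level; the output is called rates of decay, overall and by HIV status, booster type and baseline CD4 count. Sensitivity analyses are listed as not applicable.

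Pre-booster tests will be in the data. Section 6 says of the patients: "These individuals will be followed from vaccination until study end". The entry test in Section 5 ("Received a Roche SARS-CoV-2 Semi-Quant Spike Ig AB test after full vaccination as usual clinical care") may precede any booster. Section 6, Study Endpoints, adds that non- and low-responders "were offered optional booster vaccinations with subsequent antibody response measurement post vaccination as standard of care".

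**The concern.** A rate of decay after the booster needs values from after the booster. A rule satisfied by one value on each side of it, followed by one straight line through the values, describes a different quantity: the net change across a period that contains the booster. For a patient with just those two tests, the reported decay is positive whenever the titre rose.

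Objective #4 is secondary and descriptive, so no test decision depends on it. But the slope is its main result, and two analysts could follow the same text and report slopes of opposite sign. On the all-values reading, slopes by HIV status, booster type and CD4 count could also differ because the strata were retested at different rates, with no difference in decay.

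**Working it through.** The plan states no expected slope, titre distribution, test dates or retest numbers for Objective #4, so there is no figure to reproduce. Every titre, test date, half-life and boost size below is assumed. Slopes are U/mL per 30 days.

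**One patient by hand.** Formula: slope = 30 × Σ(t − t̄)y / Σ(t − t̄)², with t in days from the booster. Tests fall at days -20, +36 and +126. With a 60-day half-life, the third value is 1,000 × 0.5^(90/60) = 354.

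- First two tests only, 100 then 1,000: (1,000 − 100)/56 × 30 = **+482**.
- All three tests: t̄ = 47.33; deviations -67.33, -11.33, +78.67; Σ(t − t̄)² = 10,850.7; Σ(t − t̄)y = -6,733.3 − 11,333.3 + 27,848.0 = 9,781.3; slope = 9,781.3/10,850.7 × 30 = **+27**.
- The two post-booster tests only: (354 − 1,000)/90 × 30 = **-215**.

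The result depends on the earlier history:

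| Values before the booster | All-values slope | Post-booster slope |
|---|---|---|
| 100 at day -20 | +27 | -215 |
| 400 at day -140, 100 at day -20 | +17 | -215 |
| 1,000 at day -140, 100 at day -20 | -51 | -215 |
| 2,000 at day -140, 100 at day -20 | -164 | -215 |
| 2,000 at day -20 | -327 | -215 |

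The last patient falls throughout, and the all-values slope is too steep.

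**Pooled simulation.** 20,000 patients per scenario (for precision, not the study size) and 56 scenarios per set: 7 retest settings × 2 half-lives (60, 120 days) × 4 boost sizes. The level is multiplied at day 14 and then decays exponentially. The first post-booster test is at days 21-60. A second follows 45-120, 90-240 or 120-300 days later in 50% or 100% of patients, or in none. Log-scale noise SD is 0.2. The fit to all values is compared with the same raw-scale fit to post-booster values only; ratio means the first slope divided by the second.

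- **Set A:** one pre-booster test 1-60 days before the booster, lognormal with median 120 and log-SD 0.8, cut at 250; boost 3- to 20-fold. 31 of 56 all-values slopes are positive; the other 25 have ratio 0.05 to 0.48.
- **Set B:** Set A plus one test 90-180 days earlier. 24 positive; ratio -0.64 to 1.23; 4 too steep; 5 within 20%.
- **Set C:** as Set B, uncapped, median 1,000, boost 1.5- to 5-fold. 4 or 5 positive depending on the seed; ratio -0.25 to about 2.7; about 19 too steep; 11 within 20%.

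Counting time from initial vaccination instead of the booster changes little: 31, 24 and 4 positive.

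**Strata with identical decay** (60-day half-life, second test 90-240 days after the first, 20% against 80% retested):

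| Setting | All values | Post-booster only |
|---|---|---|
| Set A, 10-fold boost | +32 against -18 | about -124 against -118 |
| Set B, 10-fold boost | -6 against -23 | about -124 against -118 |

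At a 5-fold boost in Set B the all-values contrast nearly vanishes (-35 against -34).

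**What restriction to post-booster values does not cure.** With a 60-day half-life and tests 90 days apart, the raw slope is (0.5^1.5 − 1)/90 × 30 = -0.2155 times the first level: -65 from 300 U/mL and -215 from 1,000. From 1,000 with tests 180 days apart it is (125 − 1,000)/180 × 30 = -146. Across Set A boost sizes and retest intervals at that half-life, with half the patients retested, the pooled post-booster-only slope ran from about -31 to about -357. The log-scale slope stayed near -0.345 per 30 days, against a true value of -ln 2 × 30/60 = -0.347.

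**The case against.** The strongest reply is that the heading governs. The two-test phrase says who is analysed, not which values are modelled, and nothing states that pre-booster values enter the regression. This stands in part: a reader might infer that the plan certainly mixes rise and decline, and the documents do not establish that. But the reply does not rescue the text. If only post-booster values are fitted, a patient with one post-booster test is admitted or refused on the strength of another test that the fit ignores. Section 9 mentions working practices for analysis specifications, but no specification in the documents settles the matter.

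A second reply is that the size is unknown. This stands. A reader might infer from Section 6 that pre-booster values are low and close to the booster, so that the slope will be reversed. That section supports low values in the non- and low-responders offered boosters, but it gives no interval between test and booster. Objective #3, from which the boosted group comes ("In the sub-population of Individuals who received a COVID vaccine booster"), is not confined to those patients either. Sets B and C show the distortion can be small or run the other way.

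A third reply is that a post-booster-only raw-scale slope also varies with boost size and retest interval under identical decay. This stands too. A reader might infer that the restriction alone makes the strata comparable; the figures above show that it does not.

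The robust variance is no answer: it changes the standard error, not what the slope estimates.

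**Conclusion.** The point holds in a conditional form. The documents establish that Objective #4 targets decline after the booster, admits patients with a single post-booster test, and leaves the fitted values and the time origin unstated. On the natural reading the slope is not post-booster decay; on the other reading the eligibility rule does not fit the analysis. Either way the text needs correcting.

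That the all-values slope mixes the two phases follows from the model and needs no assumed titres. Its direction and size do rest on assumed titres, timing, retesting, half-life and boost size. The +27 against -215 contrast is one chosen patient, and the Set A counts apply only to one late, low pre-booster test per patient.

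This should be fixed before analysis, at a priority suited to a secondary descriptive objective.

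**What to change.** State the values and the time origin for Objective #4, in Section 7 and the Synopsis, by one of two routes:

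1. Fit the slope to post-booster values only, with time measured from the booster date. Require at least two post-booster tests if a within-person slope is wanted.
2. Keep all tests and add a booster term with a separate post-booster slope.

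Report the pre-to-post change under Objective #3, which already covers antibody response after the booster. Label test timing as the independent variable.

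Either route removes the pre-booster mixing and the sign reversal it can cause. To compare decay across HIV status, booster type or CD4 strata, also fit the post-booster slope to log antibody level; otherwise boost size and retest interval can still separate strata with the same half-life.

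The cost is wording plus one data filter or one model term, with no new data. Requiring two post-booster tests leaves fewer patients and may select on who is retested. Under the second route, patients with one post-booster test inform the slope only through between-patient differences in test timing.
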